1. INTRODUCTION / SYNOPSIS

This is a pilot, phase 2, prospective, comparative study to evaluate the safety and efficacy of the combination of Levulan® Kerastick® for Topical Solution and blue light illumination using the BLU-U® Blue Light Photodynamic Therapy Illuminator (Levulan-PDT).

The study hypothesis is that post solid organ transplantation patients, highly susceptible to non-melanoma skin cancer, can be treated safely and effectively through clinical cyclic application of PDT, lessening morbidity and possible mortality for this immunosuppressed patient population.

1.1 Phase

Phase 2.

1.2 Indication

Subjects who are 3 to 24 months post solid organ transplantation.

1.3 Endpoints

- The primary endpoint will be the total number of AK/NMSC in the treatment areas compared to the control areas.
- Time to occurrence to first AK/NMSC compared to the control areas.
- Changes in karyometry from baseline in the treatment and non treatment fields.
- Changes on the sun damage scale compared to the control areas.
- Mean pain score between the treatment field locations.

1.4 Patient Population

Adults (age 18 and older) who have recently undergone a solid organ transplant and have a stable graft function. Subjects should be at risk for developing AK/NMSC due to their transplant related immunosuppression and their history of photo damage skin and/or precancerous lesions.

2. STUDY DESIGN

2.1 Phase

This is a pilot, phase 2, prospective, comparative study. Each subject will undergo split-side face and dorsal forearm/hand PDT treatment at: Day 1 (initial treatment), Day 30 (1 month after initial treatment), Day 180 (6 months after initial treatment), 1 year after initial treatment, and every 6 months thereafter for 2 additional years.

2.2 Number of centers

One; the University of Arizona Cancer Center (Phoenix, AZ)

2.3 Number of subjects

We estimate a total of 16 to 20 subjects would be enrolled in this study.

2.4 The subject participation time period

Each subject would receive treatment at the beginning of the study Day 1 (Initial treatment), Day 30 after initial treatment, Day 180 after initial treatment, 1 Year after initial treatment and every 6 months thereafter for 2 additional years. The total subject participation time period from the first to last visit will be approximately 37 months. Treatment visits are based on the Day 1 treatment visit date to the 3 year treatment visit.

3. OBJECTIVES

3.1 Primary Objective

- To examine the safety and efficacy of cyclic Levulan-PDT on primary prevention of AKs/NMSC in recently transplanted solid organ recipients.

3.2 Secondary Objectives

- To investigate pain control with Levulan-PDT in SOTR.

4. BACKGROUND AND RATIONALE

4.1 Disease/Condition

Photodynamic therapy (PDT) is a field-based therapy with well-documented clinical efficacy in the treatment of non-melanoma skin cancer (NMSC) and its precursor lesions, i.e., actinic keratosis (AK) and Bowen's disease (BD) [1-3]. There are three major components of PDT: a photosensitizer (PS), a light source, and oxygen. Individually each component is not toxic, but combined they initiate a photochemical reaction which generates singlet oxygen. In turn, this reactive oxygen species can rapidly cause significant toxicity leading to cell death [4].

4.2 Investigational Intervention

There are two types of PSs employed in PDT, systemic and topical [5]. In dermatology, PDT is primarily delivered through the use of the topical PS 5-aminolevulinic acid (ALA) or its methylated ester, methyl aminolevulinate (MAL). Only ALA is currently available in the USA and FDA approved, while MAL is used in Europe and Canada. Both ALA and MAL are precursors in the heme biosynthesis and act as prodrugs in the skin, and get converted into photoactivatable porphyrins, including protoporphyrin IX (PpIX) [1]. The excitability of these molecules coupled with their tumor-localizing properties underscores their utility as PS agents [6]. Importantly, none of the clinically approved PDs accumulate in cell nuclei, limiting their carcinogenic potential [4].

In terms of light sources, there are two types: lasers and non-laser. Non-laser light sources include light-emitting diode (LED) arrays and blue light fluorescent tubes which are widely commercially available for PDT. Only blue light is currently FDA approved for use with PDT.

4.3 Preclinical Experience

PDT in Organ Transplant Recipients (OTR)

Clinical applications for the use of PDT that have shown successful outcomes include actinic keratosis (AK), Bowen's disease (BD), and basal cell carcinoma (BCC). OTRs are at significant risk for the development of NMSC. They have between a 65- and 200-fold increased risk for the development of squamous cell carcinoma (SCC) and a 10-fold increased risk of developing BCC compared to the general population [7-10]. These patients are also at increased risk for the development of precancerous lesions including AK and BD, with AKs demonstrating a greater propensity toward malignant transformation into invasive SCC [9, 11]. Overall, NMSC and its precursor lesions tend to be more numerous, diffusely located, recurrent, and aggressive in OTRs compared to immunocompetent patients [12-17]. Not surprisingly, cutaneous malignancy is therefore the leading cause of morbidity and mortality in this immunosuppressed patient population. Given this significant disease burden, a great deal of interest has focused on the treatment and prevention of NMSC in OTRs. As a convenient and economical field-based therapy capable of treating large areas or multiple lesions simultaneously with excellent cosmetic outcomes, the use of PDT has been explored as both a primary modality for and in prevention of NMSC, and its precursors, in the OTR population.

Prevention of NMSC and Precursors

The multiplicity and widespread involvement of NMSC and precursor lesions seen in OTRs have spawned a great deal of interest in exploring the effectiveness of PDT for prevention of premalignant and malignant lesions in OTRs. Preclinical studies have substantiated this interest, with PDT demonstrating a significant preventative effect in UV-related photocarcinogenesis when delivered to accepted murine models for both SCC and BCC development [18-21].

4.4 Clinical Experience

Wulf and colleagues showed in their intra patient randomized study, a single session of MAL-PDT was delivered to 27 renal transplant patients with AKs and other skin lesions and subsequently compared to an untreated contralateral control area of similar size. Overall, the average time to occurrence for new lesions was significantly longer in the treated areas with a larger percentage of these areas remaining lesion-free after 12 months compared to untreated [22]. A similar, proof-of-concept, study examining the use of PDT in cancer prevention was also conducted in immunocompetent patients by Apalla and colleagues. Utilizing a split-face, placebo- controlled study evaluating a PDT field treatment of facial AKs, they were also able to show a significant delay in the appearance of new AK lesions in PDT-treated regions after 6 months [23, 24].

Continued use of PDT for prevention of NMSC and precursors in OTR has been documented with some success in small case series and randomized trials with varied protocols. De Graaf and colleagues were the first to examine the effect of PDT on the development of new SCCs with a large randomized intra patient controlled trial. In this study, 1–2 sessions of blue light ALA-PDT were given to a randomly selected forearm and hand of 40 OTRs, and SCC occurrence was subsequently compared to the contralateral untreated forearm and hand [25]. After 1 year of follow-up, there was a trend in favor of PDT reducing the occurrence of SCC; however, no significant difference was observed at 2 years. No debulking of lesions was performed prior to PDT. In a similarly structured study, Wennberg et al. delivered two sessions of MAL-PDT with red light over 2 weeks at study inception with single treatment follow-ups at 3, 9, and 15 months to 81 OTRs [26]. At 3 months, MAL-PDT was shown to significantly reduce the occurrence of new skin lesions, primarily AKs; however, the significance of this effect was again lost at 27 months follow-up.

Most recently, Willey and colleagues treated 12 OTRs with cyclic ALA-PDT every 4–8 weeks for 2 years [27]. They found a 79% decrease in new SCC/BD at 12 months and a 95% decrease compared to baseline at 24 months. Of note, baseline occurrence in this study was defined as the number of SCCs developed during the previous 12–24 months prior to initiation of cyclic PDT.

Togsverd-Bo et al [28] found that repeated PDT sessions in renal transplant patients could serve as primary prevention for skin dysplasia. In their randomized controlled trial, 15 patients with clinically normal skin received PDT red light at inclusion and at 6 month intervals. PDT significantly delayed the onset of AK compared to untreated areas. They observed AK in 63% of patients in untreated skin compared to 28% in PDT treated skin at 3 years.

These findings are further supported by molecular studies, which mirror the clinical response, showing that PDT can reverse or reduce field cancerization but that one single dose is not sufficient to achieve these results [29,30]. For example, Bagazgoitia and colleagues have shown that two or more treatments of PDT can

delay the appearance of AKs, reduce histological features of actinic damage, and decrease expression of early markers of carcinogenesis such as K1-67 and p53 [29]. Sun-damaged skin has a higher baseline expression level of p53 than non-sun-damaged skin, and p53 and p53 family members may be important mediators of cell death signaling in photodynamic therapy of cancer [32]. This again underscores the need for repeated PDT sessions with vigilant follow-up when using this field therapy for cancer prevention. In addition, karyometric analysis has been used successfully to detect nuclear changes from sun-damaged skin to actinic keratosis to squamous cell carcinoma, and to provide sensitive, quantitative method to assess the efficacy of prevention interventions [33-36].

Associated Risks

Pain is by far the most common, and limiting, adverse event associated with PDT. Pain most often occurs early during illumination. Standard methods to decrease pain include the use of fans and the use of non-contact cold air skin cooling device during treatment. Given the larger size, number, and involvement of lesions, pain is often significantly greater in the OTR population, especially in field cancerization areas such as the head and scalp [10, 31]. Several, well-studied, pain-relieving techniques are available to complement the delivery of PDT including use of cooling fans, intra lesional anesthetics, nerve blocks, transcutaneous electrical nerve stimulation, and modified irradiance treatment. In addition, if the cooling alone is not sufficient and pain is moderate to severe (VAS>6-7), very brief interruption in illumination can be done. Daylight PDT has also been reported to have little to no treatment related pain.

SORT are especially at risk of developing multiple, aggressive or metastatic SCC, with an associated high morbidity and mortality rate. Prevention studies have typically looked at the effect of PDT in patients who had already developed many skin cancers and who may have undergone transplantation years prior to intervention. The current protocol involves early prevention of SCC development with field therapy in high risk patients who have only recently been transplanted. The proposed intervention would be an essential benefit that could be implemented in the early overall management of these patients, and may contribute to an improved long term quality of life.

5. INVESTIGATIONAL INTERVENTION

[figure not shown]
5.1 Investigational Intervention

The investigational intervention consists of a topical solution (Levulan® Kerastick®) and blue light illumination using the BLU-U® Blue Light Photodynamic Therapy Illuminator (Levulan-PDT). Levulan-PDT is indicated for the treatment of minimally to moderately thick actinic keratosis of the face or scalp.

5.1.1 Levulan® Kerastick® for Topical Solution

Levulan® Kerastick® for Topical Solution is a porphyrin precursor, containing 20% aminolevulinic acid hydrochloride (ALA HCl) by weight in a plastic applicator device.

ALA HCl is a white to off-white, odorless crystalline solid that is very soluble in water, slightly soluble in methanol and ethanol, and practically insoluble in chloroform, hexane and mineral oil. The chemical name for ALA HCl is 5-amino-4-oxopentanoic acid hydrochloride (MW = 167.59). The structural formula is represented below:

The Levulan® Kerastick® for Topical Solution applicator consists of a plastic tube (containing two sealed glass ampules) and an applicator tip. One ampule contains 1.5 mL of solution vehicle comprising alcohol USP (ethanol content = 48% v/v), water, laureth-4, isopropyl alcohol, and polyethylene glycol. The other ampule contains 354 mg of ALA HCl as a dry solid. The applicator tube is enclosed in a protective cardboard sleeve and cap. The 20% topical solution is prepared just prior to the time of use by breaking the ampules and mixing the contents by shaking the Levulan® Kerastick® for Topical Solution applicator.

5.1.2 BLU-U Blue Light Photodynamic Therapy

The BLU-U Blue Light Photodynamic Therapy Illuminator (Dusa Pharmaceuticals, Inc.) produces a photodynamic response with 20% ALA at 10 J/cm² for 1000 seconds. BLU-U peak absorption wavelength occurs at 417±5 nm and the maximum absorption peak for porphyrins occurs at 410 nm.

5.2 Investigational intervention supply

The Levulan® Kerastick® for Topical Solution is a single-unit dosage form, supplied in packs of 6. Levulan® Kerastick® for Topical Solution will be supplied by the manufacturer (Dusa Pharmaceuticals, Inc) specifically for the purpose of this study.

5.3 Investigational Intervention Accountability

Levulan® Kerastick® will be supplied directly to the Principal Investigator, [name], at the UACC dermatology clinic for use in this study. The principal investigator will be responsible for ordering Levulan® Kerastick® from the manufacturer, assuring proper storage of the medication, maintaining appropriate inventory and other necessary records, and assuring safe disposal of the medication. Levulan Kerastick (Active ingredient 5-ALA) is a nonhazardous medication and does not have special handling or disposal requirements. The only role of the pharmacy will be to receive the medication upon delivery and provide it to the principal investigator. The receipt of shipment, dispensing and return or destruction records will be tracked using the Investigational Agent Accountability Record or other applicable and similar record.

5.4 Storage

The Levulan® Kerastick® for Topical Solution will be stored between 20°-25 °C (68°-77 °F); excursions permitted to 15°-30 °C (59°-86 °F). The Levulan® Kerastick® for Topical Solution will be stored in the clinical trial office medication storage at UACC Phoenix.

5.5 Preparation

Preparation and application of Levulan-PDT solution will be conducted according to the intervention package insert:

<http://www.dusapharma.com/levulan-product-information.html>

The BLU-U® Blue Light Photodynamic Therapy Illuminator will be used according to the manufacturer Operating Manual: <http://www.dusapharma.com/assets/files/blu-u-manuals/MAN-1211AW-EN%20Rev%20G.pdf>

5.6 Handling

The Levulan® Kerastick® for Topical Solution should be used immediately following preparation (dissolution). Application must be completed within 2 hours of preparation. An applicator that has been prepared must be discarded 2 hours after mixing (dissolving) and, if needed, use a new Levulan® Kerastick® for Topical Solution.

6. SUBJECT ELIGIBILITY

Investigators will maintain an electronic subject log (in the UACC OnCore system) of all potential (i.e. consented) study subjects, which will include demographics, informed consent, eligibility, treatment assignment, on treatment, off treatment, follow up, and off study dates.

6.1 Inclusion Criteria

- a. Males or females, at least 18 years of age.
- b. Received solid organ transplant (kidney or other).
- c. 3-24 months post-transplant (any number of transplant).
- d. Time interval of at least 6 days duration where complications such as rejection episodes, viral infections, surgical interventions and therapies with mono or polyclonal antibodies are ruled out by the transplant team.
- e. No prior history of NMSC in the treatment fields.
- f. No AK/Bowen's disease in the treatment fields within the last 3 months.

- g. Moderate to severe sun damage.
- h. Be willing to forego other interventions in the treatment fields than the ones approved by the investigator that would interfere with the protocol or evaluation of the study medication.

6.2 Exclusion Criteria

- a. Patients with Fitzpatrick's scale skin type IV-VI (see appendix 4).
- b. Cutaneous photosensitivity to wavelengths of 400-450 nm, porphyria or known allergies to porphyrins.
- c. Known sensitivity to any of the components of the Levulan® Kerastick® for Topical Solution.
- d. Prior use of topical or systemic therapies that might interfere with the evaluation of the study medication during the study, within a 3 month washout period from the time of the screening visit.
- e. Unable to return for follow-up visits and tests.
- f. Any condition or situation which in the Investigator's opinion may put the subject at significant risk, could confound the study results, or could interfere significantly with the subject's participation in the study.

6.3 Enrollment

All subjects who complete the screening period of the study will be registered and assigned a unique sequential subject identification number. This number will be used to identify the subject throughout the clinical study and will be used on all applicable study documentation related to that subject. The subject identification number will remain constant throughout the study.

The written informed consent document(s) must be signed and personally dated by the subject or by the subject's legally authorized representative, and completed to a fully executed informed consent document and processed per the institution standard operating procedures.

Before subjects may be entered into the study, a copy of the written institutional review board (IRB) approval of the protocol, informed consent form (ICF), and all other applicable subject information and/or recruitment material must be on file at the institution.

7. STUDY PLAN

7.1 Intervention Regimen

Levulan® Kerastick® for Topical Solution will be applied to a designated area for 1 hour without occlusion prior to illumination with blue light using the standard FDA approved treatment time for the BLU-U device of 16 minutes 40 seconds. Each subject will be randomized to undergo treatment to one side face and one dorsal forearm/hand treatment, while the other side will serve as untreated control. Treatments will be conducted at the beginning of study Day 1 (Initial Treatment), Day 30 after the initial treatment (\pm 3 days), Day 180 after initial treatment (\pm 30 days), 1 year after the initial treatment (\pm 30 days), and every 6 months (\pm 30 days) thereafter for 2 additional years.

7.2 Pre-medications

Pretreatment will consist of cleaning the skin with 70% isopropyl alcohol and using 3 M prep tape to prepare treatment area prior to Levulan® Kerastick® for Topical Solution application.

7.3 Rescue Medications

Not Applicable

7.4 Excluded medications/treatments

No formal studies of drug interactions with Levulan® Kerastick® for Topical Solution with other drugs have been conducted. During controlled clinical studies, there were no drug-specific interactions noted. However, it is possible that concomitant use of other systemic photosensitizing agents such as griseofulvin, thiazide diuretics, sulfonylureas, phenothiazines, sulfonamides and tetracyclines may increase the photosensitizing effects of Levulan-PDT. Subjects using other photosensitizing agents will be asked to forgo other interventions in the treatment fields while participating in this study.

8. REQUIREMENTS FOR TREATMENT

8.1 Standard intervention

Levulan® Kerastick® for Topical Solution will be applied to the designated area for 1 hour without occlusion prior to illumination with blue light using the BLU-U for 16 minutes 40 seconds (FDA approved treatment time). Each subject will undergo treatment on one side face and dorsal forearm and hand treatment, while the other side will serve as an untreated control. Treatments will be conducted at the beginning of study Day 1 (Initial Treatment), Day 30 after the initial treatment (\pm 3 days), Day 180 after initial treatment (\pm 30 days), 1 year after the initial treatment (\pm 30 days), and every 6 months (\pm 30 days) thereafter for 2 additional years. Focal treatment procedures such as liquid nitrogen, excisional surgery, electrodesiccation and curettage or Mohs surgery,

for precancerous or skin cancers in intervention sites or control sites, will be performed as necessary.

8.2 Dose Intervention modification

Not Applicable.

8.3 IP intervention delays

Treatment delays up to 30 days due to grade 3 AEs or higher, patient health concerns, or long distance travel issues to treating facility may be allowed according to the discretion of the treating physician. Reason for treatment delays should be documented. Treatment delays will not be counted towards the next treatment time-point (all subsequent treatment schedules will not be interrupted or changed due to a delay).

8.4 Definition of a Dose Limiting Toxicity (DLT)

Not Applicable.

9. STUDY PROCEDURES

9.1 Screening

Potential subjects will enter the screening period of the study after a completely executed informed consent has been obtained. Please see schema section 26.

9.2 Registration/Randomization

All regulatory requirements must be in place prior to subject registrations.

UACC subject identification numbers will begin with 100 and will be assigned sequentially.

9.3 On Intervention

Please refer to study schema in section 26 of this protocol for procedures while subjects are on treatment.

9.4 End of Intervention

Subjects will have their last PDT treatment at visit 9 which will be considered off treatment when the visit is completed.

9.5 Follow up

There are no specific “Follow up” visits other than the Off Study (or End of Study) follow-up visit. Please refer to section 9.7 for more details.

9.6 Early Treatment Termination

Early treatment termination visits/procedures will be conducted when the subject decides to withdraw from the study or the PI deems it necessary to end the treatment. Procedures that will be completed during the early termination visit are outlined in the Schema table Section 26.

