9.7 Off Study

Subjects will be considered off study when all planned treatment and follow-up visits have been completed, unless death or withdrawal of consent to continue participation occurs. The end of study visit will be conducted per the schema in section 26.

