15. REMOVAL OF SUBJECTS

Subjects have the right to withdraw from the study at any time and for any reason without prejudice to their future medical care by the physician or at the institution. If this occurs, the investigator, or designee, is to discuss with the subject the safe and appropriate processes for discontinuation from the investigational treatment.

The investigator or designee must document the change in status of the subject's participation in the study and as applicable, the level of follow up that is agreed to by the subject (i.e. agrees to follow up exams, adverse event review, but not to further treatment and/or procedures).

Subject withdrawal of consent for a study indicates that the subject does not wish to receive further protocol required therapies or procedures, and the subject does not wish to, or is unable to continue further study participation. Subject data only up to the time when consent is withdrawn will be included in the analysis of the study.

The study is expected to close after all patients have been treated for 3 years.

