16. STATISTICAL CONSIDERATIONS

Characteristics of study subjects will be summarized by appropriate abstract statistics, including frequency, proportion and 95% Clopper-Pearson confidence interval (CI) for the proportion for categorical variables, median, and range for continuous variables.

Evaluable subjects for safety outcome measures will be those who complete any study visits or those who discontinue the study treatments due to adverse events (AE).
Evaluable subjects for efficacy outcome measures will be those who complete all study visits. At least 15-16 evaluable subjects for each of these analyses are expected.

Primary efficacy outcome measure will be the difference in the total number of AK/NMSC in the treatment areas compared to the control areas. All unique AK/NMSC

observed during the 3 year study period will be identified and summed in each area. The statistical significance of the difference will be tested using the Wilcoxon Signed-Rank Test.

Secondary safety and efficacy measure: Time to the occurrence of the first AK/NMSC in the control versus treated areas will be estimated using the Kaplan-Meier estimate. Changes in the p53 staining from baseline to end of treatment will be evaluated using McNemar's Test. Mean pain scores (VAS) and photo damage scale global scores of the study population will be compared with each respectively using Wilcoxon Signed-Rank Test.

Sample Size Determination: Safety will be evaluated using a one-sided confidence interval (as the lower bound is not of interest). At least fourteen patients will be evaluable for safety. If none of the patients have an adverse primary safety outcome, the upper bound of a 95% one-sided confidence interval is < 20%.

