26. SCHEMA OR STUDY SCHEDULE

Study Procedures	Screening/ Baseline ^A	On Study Treatment ^B								Early Termination	End of Study ^c
		Day 1	Day 30	Day 180	12 Month	18 Month	24 Month	30 Month	36 Month		
Visits	1	2	3	4	5	6	7	8	9	ET	EOS
Eligibility Verification	x										
Informed Consent	x										
Registration	x										
Medical History ^D	x										
Physical Exam ^E	x										
Concomitant medications	x	x	x	x	x	x	x	x	x		
Levulan-PDT		x	x	x	x	x	x	x	x		
Adverse events		x	x	x	x	x	x	x	x	x	
Punch Biopsy ^F		x							x		
VAS Scale ^G		x	x	x	x	x	x	x	x		
Sun Damage Scale ^H		x	x	x	x	x	x	x	x	x	x
Photographs ^I		x	x	x	x	x	x	x	x	x	x

^A Screening may be conducted within 28 days before first treatment.

^B Treatments may be conducted \pm 3 days for Day 30 treatment and \pm 30 days for Day 180, 1 year, 1.5 year, 2 year, 2.5 year, and 3 year visits respectively. Treatment visits are based on the Initial Day 1 treatment visit.

^C 3 months (\pm 30 days) after the last treatment.

^D Medical history including past medical, meds, allergies, social and HPI will be done.

^E Physical exam will consist of vital signs (blood pressure & pulse), and a full treatment area skin exam.

^F Punch biopsies will be used for karyometric analysis between baseline and end of treatment.

^G For more information about the VAS Scale, please refer to Appendix 1.

^H For more information about the Sun Damage Scale, please refer to Appendix 2.

^I For more information about digital photography, please refer to Appendix 3.

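### Sections 9.4 to 9.7, 15, 16 and 26 do not agree on whether a subject who stops PDT without withdrawing consent is still observed to month 36

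*Combined protocol and SAP*

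**What the plan says.** **Provisions that suggest observation ends soon after PDT stops**

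- Section 9.6 triggers the Early Termination visit "when the subject decides to withdraw from the study or the PI deems it necessary to end the treatment". One of these is a change of study status, the other a change of treatment status. Both lead to the same visit.
- Section 9.5 provides for no follow-up visits "other than the Off Study (or End of Study) follow-up visit".
- Section 26, footnote C, places End of Study 3 months (plus or minus 30 days) "after the last treatment".
- In the section 26 table every visit from Day 1 to month 36 includes Levulan-PDT, and no exam-only visit is listed. The Early Termination column marks adverse events, sun damage scale and photographs. The End of Study column marks only the last two.

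**Provisions that suggest it continues**

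- Section 9.7: "Subjects will be considered off study when all planned treatment and follow-up visits have been completed, unless death or withdrawal of consent" occurs.
- Section 15 asks staff to document the follow-up a subject accepts, and gives as its example one who "agrees to follow up exams, adverse event review, but not to further treatment and/or procedures".
- Section 9.4 places the last PDT at visit 9, the month 36 visit.
- Section 10.1 calls for the 3-year forearm biopsies in all patients.
- Section 26, footnote B, counts the visit calendar from Day 1.

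**What depends on it**

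Under section 16 the primary measure takes all unique AK/NMSC "observed during the 3 year study period will be identified and summed in each area" and compares the two sides by a Wilcoxon signed-rank test. The same section limits the efficacy set to subjects who attend every study visit.

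**The concern.** The primary measure is a within-person lesion count over three years. Photographing both sides does not require that PDT continue, so a subject who stops PDT can still supply a complete pair. Section 4.4 names pain as the most common and limiting adverse event of PDT, and as often greater in transplant recipients, so stops for tolerability are foreseeable.

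As written, site staff have no visit, list of assessments or end date for the subject whom section 15 describes. If they follow sections 9.5, 9.6 and footnote C, observation of both sides ends early and the section 16 rule removes the subject from the efficacy analysis. The result then describes subjects who stayed on PDT, not everyone who started it. In a pilot of 16 to 20 subjects each lost pair counts.

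**Working it through.** **Figures in the plan.** The documents state no dropout rate, no rate of stopping PDT and no efficacy power, so there is no planned figure on this point to reproduce. The only sample-size figure is for safety: 0 events in 14 gives a one-sided 95% upper bound of 1 − 0.05^(1/14) = 19.3%, which agrees with the stated value of under 20%. It does not bear on the visit schedule.

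**Unobserved time.** Inputs: a 36-month window (section 16), session months from section 26, and End of Study 3 months after the last treatment (footnote C). Reading that phrase as the last session received, at month m:

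unobserved months = 36 − (m + 3)

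The 30-day window moves each result by about 1 month.

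| Last session (month) | End of Study (month) | Unobserved months (with window) | Scheduled visits left |
|---|---|---|---|
| 0 (Day 1) | 3 | 33 (32–34) | 7 |
| 1 | 4 | 32 (31–33) | 6 |
| 6 | 9 | 27 (26–28) | 5 |
| 12 | 15 | 21 (20–22) | 4 |
| 18 | 21 | 15 (14–16) | 3 |
| 24 | 27 | 9 (8–10) | 2 |
| 30 | 33 | 3 (2–4) | 1 |

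If the stop is decided only at the next scheduled visit, the Early Termination assessments fall there and are the last observation. For last sessions at month 1, 6, 12, 24 and 30 the next visits are at 6, 12, 18, 30 and 36, so the losses become 30, 24, 18, 6 and 0 months.

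**What that time could contain (illustration only).** Section 4.4 cites a three-year trial with AK in 63% of patients on untreated skin and 28% on PDT-treated skin. Assuming constant hazards:

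- untreated: −ln(1 − 0.63)/36 = 0.0276 per month
- treated: −ln(1 − 0.28)/36 = 0.0091 per month

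For a last session at month 6 (End of Study at month 9):

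- untreated: 1 − exp(−0.0276 × 9) = 22.0% have a first AK by then, leaving 63 − 22 = 41 points, or 65% of the 63
- treated: 7.9% by then, leaving about 20 of 28 points

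For a last session at month 12 (End of Study at month 15), 29 of 63 points (46%) and 15 of 28 points come later. For month 24 the untreated share is 17%. These are proportions with a first AK, not the lesion counts of the primary measure, and the trial does not plan on them.

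**Room for loss.** Enrolment is 16 to 20 (section 2.3), and section 16 expects at least 15-16 evaluable. With 16 enrolled, 16 − 16 = 0 to 16 − 15 = 1 subject can be lost. With 20 enrolled, 20 − 16 = 4 to 20 − 15 = 5 (20% to 25%).

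**The case against.** The strongest reply is that the documents do not forbid continued observation. Section 9.7 can be read as keeping a consenting subject on study to the end of the planned visits. Section 15 allows exams by agreement, footnote B fixes the calendar from Day 1, and section 10.1 expects the 3-year biopsy in everyone. Section 9.4 puts the last PDT at visit 9, so footnote C could mean 3 months after the planned month 36 session, in which case the gaps tabulated above do not arise from End of Study timing. This stands. A reader might infer that data after a stop are never collected, but the texts conflict and do not support so firm a statement. Nor does the permission solve the problem: it sets no visits, assessments or end date, and case-by-case follow-up in so small a trial would give uneven data.

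A reader might also infer that safety review ends when PDT stops. It does not. Adverse events are assessed at the Early Termination visit, section 11.5 records all of them with their outcome, and section 15 allows further review by agreement. What is missing is a scheduled review after that visit.

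A third reply is that the section 16 all-visits rule would exclude these subjects anyway. That is correct: extra visits alone would not repair the primary analysis. But changing the analysis set alone cannot recover lesions that nobody recorded. Both need amending.

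Finally, both sides of a subject are lost together, so the comparison within subjects is not unbalanced.

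**Conclusion.** The provisions on observation after PDT stops are inconsistent and should be reconciled. On the reading that ties End of Study to the last session received, the unobserved time runs from about 32 months after a stop at month 1 to about 3 months after a stop at month 30. The early-stop figures should not be taken as typical, because later stops lose little. Combined with the section 16 rule, the effect is a smaller n and an efficacy estimate in subjects who tolerated PDT.

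The number of subjects affected and the loss of power cannot be computed from the documents. The point applies only to subjects who stop PDT without withdrawing consent; after withdrawal, section 15 limits the data to that date. It merits correction because the remedy is inexpensive, not because a large bias has been shown.

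**What to change.** 1. **Section 9.6:** separate stopping PDT from withdrawing consent. Keep the Early Termination assessments (adverse events, photographs, sun damage scale) at the time PDT stops. For subjects who have not withdrawn consent, continue the remaining section 26 visits to month 36 without PDT and VAS, within the follow-up agreed under section 15.
2. **Section 9.5 and footnote C:** amend section 9.5 to match, and time End of Study from the month 36 visit for these subjects.
3. **Section 10.1:** state whether the month-36 biopsy applies to them, subject to consent.
4. **Section 16:** make efficacy-evaluable status depend on attending assessment visits, not on receiving every PDT session. Report full-course completers as a sensitivity analysis.

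The cost is wording in these sections, plus at most seven visits per affected subject (one after a stop at month 30), on the existing calendar and with existing procedures. The primary estimate would then include partial-course subjects and may be somewhat diluted, which the sensitivity analysis would show. No rule on when to stop PDT is changed.
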